5.1.2 Stereotactic Ablative Radiation Therapy (SABR)

SABR will be administered concurrently during the second cycle of the anti-PD-L1 Atezolizumab (week 4) and in case of first progression in patients with lung cancer and sarcoma.

SABR will be delivered using 6MV photons or other energies with standard field encompassing tumour. Hypofractionated SABR will be delivered within 3 fractions in total to a total of 45 Gy (3 fractions of 15 Gy). In order to comply with the QUANTEC normal tissue tolerance guidelines, the dose may be adapted according to dosimetric constraints but must never be inferior to 33 Gy in fractions of 11 Gy.

Tumour size will be ≤ 4 cm according to recent imaging (CT, MR or PET).

The radiation dose will be prescribed to the 90% isodose line in order to deliver 95% of the planned dose to 95% of the planned tumour volume (PTV).

Patients will be eligible if dose constraints to organ at risk are respected.

SABR software tools and accurate dose calculations allow for better targeting of tumours, while providing motion management for precise dose delivery. Generally, this technique includes:

- 4D CT data integration for moving target such as lung tumours
- Patient's immobilization with a vacuum cushion.
- Precise type B dose calculation algorithm (Monte Carlo, or other type B dose calculation algorithms)
- Monitoring of respiratory motion.
- Real-time detection and compensation of tumour motion (on-board CT)

The definition of volumes will be in accordance with ICRU Reports #50, #62 and #83.

SABR will be given on alternate days and only type B dose calculation algorithms will be accepted.

Margins from GTV (or ITV) to PTV are of 5 - 10 mm to account for set-up error and organ motion.

Any organ that is traversed by part or all of a beam should be contoured so that the dose it receives can be assessed. Organs should be outlined by the treating radiotherapist (or dosimetrist and checked by treating radiotherapist). Dose constraints are adapted to the standard recommendations (cf Appendix 1: Rules for SABR administration according to tumour location).

5.2 Dosage and schedule of treatment

5.2.1 Atezolizumab

The dose of atezolizumab will be 1200 mg administered by intravenous infusion every 3 weeks (21 [+ 3] days).

Administration of atezolizumab will be performed in a setting with emergency medical facilities and staff who are trained to monitor for and respond to medical emergencies.

The initial dose of atezolizumab will be delivered over $60 (\pm 15)$ minutes. If the first infusion is tolerated without infusion-associated adverse events, the second infusion may be delivered over $30 (\pm 10)$ minutes. If the 30-minute infusion is well tolerated, all subsequent infusions may be delivered over $30 (\pm 10)$ minutes.

For the infusion, the patient's vital signs (heart rate, respiratory rate, blood pressure, and temperature) should be determined within 60 minutes before, and 30 (\pm 10) minutes and after the infusion. For subsequent infusions, vital signs will be collected within 60 minutes before infusion and at the end of the infusion, if clinically indicated.

Patients will be informed about the possibility of delayed post-infusion symptoms and instructed to contact their study physician if they develop such symptoms.

No premedication will be allowed for the first dose of atezolizumab. Premedication may be administered for Cycles ≥ 2 at the discretion of the treating physician. The management of infusion-related reactions will be performed according to severity as described in section 5.3.2.6

In the event of a suspected anaphylactic reaction during study drug infusion, the following procedures should be performed:

- Stop the study drug infusion
- Apply a tourniquet proximal to the injection site to slow systemic absorption of study drug. Do not obstruct arterial flow to the limb.
- Maintain an adequate airway
- Administer antihistamines, epinephrine or other medications as required by patient status and directed by the physician in charge
- Continue to observe the patient and document observations

Guidelines for dosage modification, treatment interruption or discontinuation, and the management of specific adverse events are provided 5.3.2.

Any overdose or incorrect administration of study drug should be noted on the Study Drug Administration Case Report Form (CRF). AEs associated with an overdose or incorrect administration of study drug should be recorded on the Adverse Events CRF pages.

Cessation of immunotherapy for long-term responders

The optimal duration of treatment for immunotherapy remains debated. Phase 3 clinical trials in NSCLC and melanoma were designed with treatment until progression or unacceptable

toxicity. Responses however can be durable after discontinuation in patients who received receiving 2 years of treatment.

In melanoma patients, the KEYNOTE 006 trial compared pembrolizumab (10 mg/kg2 weekly or 3 weekly) to ipilimumab (3 mg/kg 3 weekly for 4 doses) and trial design stipulated planned discontinuation of treatment at 24 months or earlier if confirmed complete response (CR). If discontinued at 24 months, patients were allowed to recommence 12 months of pembrolizumab upon progressive disease. Of the 834 patients enrolled, 103 of 566 (19%) patients receiving one of the two pembrolizumab arms received the full 24 months of treatment and discontinued. At a median follow up of 20 months post-discontinuation, 86% of these patients had ongoing responses [Robert].

In previously treated non-small cell lung cancer (NSCLC) patients with PD-L1 positive tumors (TPS >1%), the KEYNOTE 010 trial randomized to one of three arms; pembrolizumab 10 mg/kg3 weekly, pembrolizumab 2 mg/kg3 weekly or docetaxel for 35 cycles (2 years). At a median follow up of 42.6 months, 79 of 690 (11%) enrolled patients had completed the 35 cycles being 2 years of treatment and of these, 95% had achieved CR or partial response (PR) as best overall response [Herbst].

This data supports the evidence of durability of response upon discontinuation. Durability post-discontinuation due to toxicity is also a feature of immunotherapy. In patients who have not progressed after 2 years of anti-PD(L)1 treatment, it is then appropriate to consider and discuss treatment discontinuation.

Therefore, if active disease is not detected on CT or PET/CT scans discontinuing anti-PD-L1 therapy after 24 months will be proposed.

5.2.2 SABR

It will be administered concurrently during the second cycle of the anti-PD-L1 (week 4) and in case of a first radiological progression as per RECIST v1. in patients with lung cancer and sarcoma.

SABR will be delivered using 6MV photons or other enegies with standard field encompassing tumour. Hypofractionated SABR will be delivered with an equivalent biologic dose > 80 Gy (45 Gy in 3 fractions of 15 Gy). The recommended fractionation is 45 Gy (3 fractions of 15 Gy) but shall be adapted upon normal tissue tolerance constraints (Annex 1). Total duration of radiotherapy must not exceed eight days and a window of \pm 3 days allowed to start the treatment.

Tumour size will be ≤ 4 cm according to recent imaging (CT or PET).

The radiation dose will be prescribed to the 90% isodose line in order to deliver 95% of the planned dose to 95% of the planned tumour volume (PTV). The dose used to treat a given metastasis will be based on the location of the metastasis, as normal tissue toxicity is likely to arise from the organs at risk surrounding the metastasis.

5.3 Adaptation of doses and interruption of treatment

5.3.1 Doses modifications for SABR

Management of treatments during protocol treatment toxicity according to the NCI-CTCAE scale (CTCAE v 5.0)

Cutaneous toxicity (radiotherapy-associated dermatitis)

- Grade 4, SABR must be discontinued

Pulmonary toxicity (dyspnea, pneumopathy)

- **Grade 3/4,** SABR and atezolizumab must be interrupted. Patients must then be reassessed every week

SABR must only be discontinued in the event of a grade or 3 or 4 pharyngo-oesophageal, cutaneous or pulmonary reaction in the irradiated field. SABR and/or atezolizumab must only be reintroduced after the toxicity has recovered to grade 2 or less.

Digestive toxicity within the field:

Medical management includes treating diarrhea, dehydration, malabsorption, and abdominal or rectal discomfort. Symptoms usually resolve with medications, dietary changes, and rest. If symptoms become severe despite these measures, a treatment break may be warranted.

In addition to these medications, opioids may offer relief from abdominal pain. If proctitis or oesophgitis is present, steroid foam given rectally may offer relief from symptoms.

If esophagitis occurs, making oral feeding impossible, placement of a nasogastric tube must be considered.

In the event of grade 3 esophagitis that is poorly tolerated in spite of appropriate treatment, SABR can either be continued with enteral and/or parenteral feeding plus appropriate analgesic treatment, or it may be discontinued for less than 5 days until improvement (≤ grade 2 or grade 3 that is well tolerated with appropriate treatment).

- Grade 4 (oesophagitis, diarrhea, abdominal pain), SABR and atezolizumab must be interrupted. Patients must then be reassessed every week
- **Grade 3 (diarrhea, abdominal pain),** Atezolizumab must be discontinued only if symptoms do not improve despite discontinuation of SABR for 8 days.

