5.3.2.1 Pulmonary Events

Pulmonary events may present as new or worsening cough, chest pain, fever, dyspnea, fatigue, hypoxia, pneumonitis, and pulmonary infiltrates. Patients will be assessed for pulmonary signs and symptoms throughout the study and will also have CT scans of the chest performed at every tumor assessment.

All pulmonary events should be thoroughly evaluated for other commonly reported etiologies such as pneumonia or other infection, lymphangitic carcinomatosis, pulmonary embolism, heart failure, chronic obstructive pulmonary disease, or pulmonary hypertension. COVID-19 evaluation should be performed per institutional guidelines where relevant.

Table 2: Management guidelines for pulmonary events including pneumonitis

Severity	nent guidelines for pulmonary events including pneumonitis Management
Grade 1	Continue atezolizumab with close monitoring
	Re-evaluate on serial imaging
	Consider pulmonary consultation
	For grade 1 pneumonitis, consider withholding Atezolizumab
	Consider resumingon radiographic evidenceof improvement
Grade 2	 Withhold atezolizumab for up to 12 weeks after event onset. ^a
	 Refer patient to Pulmonary and infectious disease specialists and consider bronchoscopy or BAL with or without transbronchial biopsy.
	 Initiate treatment with 1–2 mg/kg/day oral prednisone or equivalent.
	 Resume atezolizumab if event resolves to Grade 1 or better within 12 weeks. ^{a, b}
	 Permanently discontinue atezolizumab and contact the principal investigator if event does not resolve to Grade 1 or better within 12 weeks.^{a, b, c, d}
	 For recurrent events, or events with no improvement after 48-72 hours of corticosteroids, treat as a Grade 3 or 4 event.
Grade 3 - 4	 Permanently discontinue atezolizumab and contact the principal investigator.^{c,d}
	 Oral or IV broad-spectrum antibiotics should be administered in parallel to the immunosuppressive treatment
	 Bronchoscopy or BAL with or without transbronchial biopsy is recommended
	 Initiate treatment with 1–2 mg/kg/day oral prednisone or equivalent.
	 If event does not improve within 48 hours after initiating corticosteroids, consider adding an immunosuppressive agent.
	 If event resolves to Grade 1 or better, taper corticosteroids over ≥ 1 month.

BAL = bronchoscopic alveolar lavage; ID = infectious disease, IVIG = intravenous immunoglobulin

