- a If corticosteroids have been initiated, they must be tapered over \geq 1 month to \leq 10 mg/day oral prednisone or equivalent before atezolizumab can be resumed.
- b Atezolizumab may be withheld for a period of time beyond 12 weeks to allow for corticosteroids to be reduced to ≤ 10 mg/day oral prednisone or equivalent. The acceptable length of the extended period of time must be agreed upon by the investigator and the Medical Monitor.
- c Resumption of atezolizumab may be considered in patients who are deriving benefit and have fully recovered from the immune-related event. Patients can be rechallenged with atezolizumab only after approval has been documented by both the investigator (or an appropriate delegate) and the sponsor.
- d In case of pneumonitis, atezolizumab should not be resumed after permanent discontinuation.

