5.3.2.3 Gastrointestinal Events

All events of diarrhea or colitis should be thoroughly evaluated for other more common etiologies. For events of significant duration or magnitude or associated with signs of systemic inflammation or acute phase reactants (e.g., increased c-reactive protein, platelet count, or bandemia), it is recommended to do the following:

- Perform sigmoidoscopy (or colonoscopy, if appropriate) with colonic biopsy with three to five specimens for standard paraffin block to check for inflammation and lymphocytic infiltrates for confirmation of the diagnosis of colitis.

Severity	Management
Grade 1	Continue atezolizumab
diarrhea or colitis	Initiate Symptomatic treatment
Contis	 Endoscopy is recommended if symptoms persist for > 7 days.
	Close monitoring
Grade 2	Withhold atezolizumab for up to 12 weeks after event onset. ^a
diarrhea or Grade 2 colitis	Initiate Symptomatic therapy
Grade 2 contis	 If strong clinical suspicion for immune-mediated colitis, initiate empiric IV corticosteroids while waiting for definitive diagnosis.
	GI consultation is recommended
	 If persists > 5 days or recurs: initiate treatment with 1-2 mg/kg/day oral prednisone or equivalent. If the event does not improve within 48 hours after initiating corticosteroids, consider adding an immunosuppressive agent.
	 Resume atezolizumab if event resolves to Grade 1 or better within 12 weeks.^{a, b}
	 Permanently discontinue atezolizumab and contact principal investigator if event does not resolve to Grade 1 or better within 12 weeks^c
Grade 3	Withhold atezolizumab. for up to 12 weeks after event onset. ^a
diarrhea or colitis	GI referral and confirmation biopsy
Contis	 Treat with IV steroids (1–2 mg/kg/day methylprednisolone or equivalent) and convert to oral steroids (prednisone 1-2 mg/kg/day or equivalent) after improvement.
	 If event does not improve within 48 hours after initiating corticosteroids, consider adding an immunosuppressive agent.
	 Resume atezolizumab if event resolves to Grade 1 or better within 12 weeks. ^{a, b}
	Permanently discontinue atezolizumab and contact the principal

Severity	Management
	investigator if event does not resolve to Grade 1 or better within 12 weeks °
Grade 4 diarrhea or	 Permanently Discontinue atezolizumab and contact the principal investigator. ^C
colitis	GI referral and confirmation biopsy

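### Sections 5.3.1 and 5.3.2 give inconsistent atezolizumab instructions for overlapping grade 3-4 pulmonary and diarrhoea events, and nothing says which section governs

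*Protocol*

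**What the plan says.** Section 5.3.1 is headed as dose modification for SABR, but it also instructs on atezolizumab. For grade 3/4 pulmonary toxicity (dyspnoea, pneumopathy), and again for grade 4 oesophagitis, diarrhoea or abdominal pain within the field, it says "SABR and atezolizumab must be interrupted. Patients must then be reassessed every week". After a sentence on pharyngo-oesophageal, cutaneous and pulmonary reactions in the irradiated field it adds "SABR and/or atezolizumab must only be reintroduced after the toxicity has recovered to grade 2 or less". For grade 3 diarrhoea or abdominal pain within the field it says "Atezolizumab must be discontinued only if symptoms do not improve despite discontinuation of SABR for 8 days".

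Section 5.3.2 covers atezolizumab-specific events.

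- **Table 2 (5.3.2.1)** permanently discontinues atezolizumab at pulmonary grade 3-4. Its grade 2 row withholds the drug and then says "Resume atezolizumab if event resolves to Grade 1 or better within 12 weeks". Footnote c lets resumption be considered after full recovery, with approval documented by investigator and sponsor. Footnote d adds "In case of pneumonitis, atezolizumab should not be resumed after permanent discontinuation".
- **The table in 5.3.2.3** says "Withhold atezolizumab for up to 12 weeks after event onset" for grade 2 diarrhoea or colitis. It repeats this, with a stray full stop, for grade 3. At grade 4 it permanently discontinues, with a footnote c in the same terms as the pulmonary one.

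Section 4.3 refers to 5.3.1 and 5.3.2 together for adverse events that preclude further study drug.

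**The concern.** Both sections tell a site what to do with atezolizumab after severe lung or bowel toxicity, and the instructions differ. SABR is given with the second atezolizumab cycle, so a severe event soon afterwards can plausibly be read under either section. Two sites that both follow the protocol could then handle the same event differently.

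Patient safety comes first. All cohorts are closed to inclusions, but treatment runs until progression or unacceptable toxicity. A second SABR course with continued atezolizumab also remains available in the lung and sarcoma cohorts, so the situation can still arise. The protocol does not say how many patients remain on treatment.

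The statistical stake is secondary. Discontinuations for adverse events are summarised under section 8.3.3, and the treatment failure rate depends on relative atezolizumab dose intensity below 75% (900/1200 mg). Both could partly reflect which section a site read.

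**Working it through.** The plan has no figure to reproduce on this point. The check sets the passages side by side.

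| Event and grade | Section 5.3.1 | Section 5.3.2 |
|---|---|---|
| Pulmonary, grade 3/4 | Interrupt, reassess weekly; reintroduction permitted at grade 2 or less | Permanently discontinue; resumption considered only after full recovery and approval; none in pneumonitis |
| Diarrhoea, grade 3 (5.3.1: within the field) | Stop only if no improvement after 8 days without SABR | Withhold for up to 12 weeks; resume at grade 1 or better |
| Diarrhoea, grade 4 (5.3.1: within the field) | Interrupt, reassess weekly | Permanently discontinue, subject to footnote c |

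1. **Pulmonary grade 3/4.** A patient improving from grade 3 to grade 2 may restart under 5.3.1. Under Table 2 the drug has been permanently discontinued, and grade 2 is itself a grade at which it is withheld. Footnote c requires full recovery, which is not grade 2.

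2. **Diarrhoea grade 3.** The word "only" in 5.3.1 means atezolizumab is not stopped at onset, while 5.3.2.3 withholds it. Reading the 5.3.1 stop as permanent does not help. First, 5.3.1 uses the same verb for short breaks in SABR. Second, a permanent stop after 8 days would still conflict with the 12 weeks that 5.3.2.3 allows for resolution.

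3. **Diarrhoea grade 4.** Both sections stop the drug; they differ on whether the stop is temporary. The digestive block of 5.3.1 gives no restart condition of its own, since the grade 2 sentence follows text on other reactions. Section 5.3.2.3 agrees with the general grade 4 rule in 5.3.2.

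4. **Overlap.** The pulmonary grade 3/4 bullet in 5.3.1 carries no field restriction. Section 5.3.2 extends to toxicities only possibly linked to atezolizumab, and 5.3.2.1 lists both dyspnoea and pneumonitis. One event can therefore meet both descriptions.

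5. **Length of interruption, in 21-day cycles.** The 8-day SABR break is 8/21 = 0.4 cycle, during which 5.3.1 need not stop atezolizumab. The 12-week limit is 84/21 = 4 cycles. Section 8.2 counts an interruption of more than 2 cycles, that is more than 2 × 21 = 42 days, as a limiting event. The same grade 3 event can stay below that limit under 5.3.1 and exceed it under 5.3.2.3. Grade 4 events are limiting either way. This shows how a count can depend on the section followed; the rule itself covers only the first 20 patients.

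**The case against.** The strongest reply is scope. Section 5.3.1 concerns SABR, its digestive block is limited to the field, and the sentence before the reintroduction condition speaks of reactions in the irradiated field. Section 5.3.2 concerns atezolizumab, and footnote c speaks of immune-related events. The protocol also directs causal work-up: tests for an immune cause in 5.3.2, evaluation for other causes in 5.3.2.1, and evaluation with biopsy in 5.3.2.3. This narrows the overlap but does not remove it, for the reasons in step 4 and because section 4.3 ranks neither section.

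A second reply is that a reader might infer opposite commands in all three combinations, and the text does not support that. The reintroduction sentence is a minimum condition, not an order to restart: a site that interrupts at pulmonary grade 3/4 and never restarts breaches neither section. At grade 4 diarrhoea both sections stop the drug. This stands. The pulmonary conflict is that one section permits what the other withholds, and the grade 4 conflict concerns permanence. Only grade 3 diarrhoea is a direct clash.

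A reader might also infer that 5.3.2 bars resumption altogether. Footnote c shows otherwise; the bar applies to pneumonitis.

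Finally, a reader might assume that in-field and immune-mediated events cannot be told apart. The protocol does not say so, and the point does not need it. It is enough that no rule says which instruction applies when an event falls under both sections.

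**Conclusion.** The inconsistency is real and should be corrected. It covers three event and grade combinations: one direct clash (grade 3 diarrhoea), one difference in the condition for resuming (pulmonary grade 3/4) and one difference in permanence (grade 4 diarrhoea). For oesophagitis and abdominal pain, which 5.3.2.3 does not name, any conflict is only with the general rules in 5.3.2.

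The main weight is patient safety. Counts of interruptions and discontinuations can depend on the section followed, but the protocol gives no event frequencies, so no effect size is claimed. The primary test and the sample size are unaffected. A reader might go further and infer a bias in progression-free survival, because section 8.3.2 has a censoring rule for patients who stop for reasons other than progression. Nothing in the protocol shows that these events would change that result.

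The conclusion assumes that some patients are still on atezolizumab or may receive a second SABR course, and that an event can be attributed to either treatment when it is managed.

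A separate minor point: 5.3.1 grades toxicity by CTCAE v5.0, while the toxicity endpoint in section 7.2.2 uses v4.03. No grade definition for these events has been shown to differ between the two.

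**What to change.** The sponsor's medical lead should reconcile 5.3.1 with 5.3.2.1 and 5.3.2.3 so that each event and grade carries one atezolizumab instruction, including the condition for any resumption. The protocol should state, in 5.3 or 4.3, which section governs when an event falls under both. Which clinical rule to adopt is for the medical lead; none is proposed here. At the same time, the CTCAE version in 5.3.1 should be aligned with that of the toxicity endpoint.

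The cost is a protocol clarification or amendment and a letter to sites. The sample size and the primary analysis need no change.

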- The investigator should consider the benefit □risk balance for a given patient prior to further administration of atezolizumab. Atezolizumab should be permanently discontinued in patients with life-threatening immune-related adverse events. Resumption of atezolizumab may be considered in patients who are deriving benefit and have fully recovered from the immune-mediated event. The decision to rechallenge patients with atezolizumab should be based on the investigator's benefit-risk assessment of the benefits and risks and documented by the investigator. The Medical Monitor is available to advise as needed..

Guidelines for managing patients who experience selected adverse events are provided in the following sections. Management guidelines are presented by adverse event severity based on the National Cancer Institute Common Terminology Criteria for Adverse Events (NCI CTCAE).

